6.1. Subject Accountability

The disposition of subjects will be summarized for the 205MS301-303 ITT population, including the number and percentage of subjects who received treatment, discontinued treatment, or withdrew from the study. Reasons for withdrawal or treatment discontinuation will also be summarized.

The disposition of subjects enrolling from Study 205MS203 or Study 205MS302 Into Study 205MS303 will be summarized, including the number and percentage of subjects who received treatment, discontinued treatment, or withdrew from the study. Reasons for withdrawal or treatment discontinuation will also be summarized.

6.2. Demography and Baseline Disease Characteristics

6.2.1. Demography and Baseline Disease Characteristics for the 205MS301-303 ITT Population

Demographic data collected at the start of 205MS301 study (205MS301 Baseline) and at the start of 205MS303 study (205MS303 Baseline) for the 205MS301-303 ITT population will be summarized by previous 205MS301 treatment group and for all subjects combined. Demographic data will include age at baseline (years), age category (<18, 18-19, 20-29, 30-39, 40-49, 50-55, and >55, also ≤ 35 , >35), gender, height, race category and weight (kg).

Medical history (collected at the start of 205MS301 and updated since) will be summarized by prior treatment group in the 205MS301 study and for all subjects combined for the 205MS301-303 ITT population. Other baseline characteristic data at 205MS301 Baseline and at 205MS303 Baseline (e.g., EDSS test scores, the number of relapses in a year prior to baseline, MRI endpoints) will also be summarized for the 205MS301-303 ITT population using descriptive statistics by 205MS301 treatment group and for all subjects combined.

EDSS test score at the 205MS303 baseline is defined as score at the most recent assessment prior to the first dose in 205MS303, excluding assessments occurring within 29 days after a relapse onset.

The following MRI characteristics will be presented for the 205MS301 baseline and the 205MS303 baseline in the 205MS301-303 ITT population: the number of Gd lesions, the number and volume of T2 hyperintense lesions, and the number and volume of T1 hypointense lesions.

6.2.2. Demography and Baseline Disease Characteristics for the 205MS203-303 ITT Population

Demographic data collected at the start of 205MS303 study (205MS303 Baseline) for the 205MS203-303 ITT population will be summarized for all subjects combined.

Medical history (collected at the start of 205MS201 and updated since) will be summarized for all subjects combined for the 205MS203-303 ITT population. Other baseline characteristic data at 205MS303 Baseline (e.g., EDSS test scores, the number of relapses in a year prior to baseline) will

	Protocol 205MS303 Statistical Analysis Plan	Final Version 1.0
---	--	--------------------------

also be summarized for the 205MS203-303 ITT population using descriptive statistics for all subjects combined.

6.2.3. Demography and Baseline Disease Characteristics for the 205MS302-303 ITT Population

Demographic data collected at the start of 205MS303 study (205MS303 Baseline) for the 205MS302-303 ITT population will be summarized for all subjects combined.

Medical history (collected at the start of 205MS302 and updated since) will be summarized for the 205MS302-303 ITT population. Other baseline characteristic data at 205MS303 Baseline (e.g., EDSS test scores, the number of relapses in a year prior to baseline) will also be summarized for the 205MS302-303 ITT population.

6.3. Extent of Exposure

6.3.1. Extent of Exposure for the 205MS301-205MS303 Study Population

The number of doses of DAC HYP received in 205MS303 and in total, per subject, will be summarized for the 205MS301-303 ITT population by prior treatment group in the 205MS301 study and for all subjects combined.

Time on study (days) will be computed for each subject as (date of study completion or withdrawal) – (date of first dose in 205MS303) + 1 day.

6.3.2. Extent of Exposure for the 205MS203-205MS303 Study Population

The number of doses of DAC HYP received in the 205MS303 study and in total, per subject, will be summarized for all subjects combined.

Time on study (days) in the 205MS303 study will be computed for each subject as (date of study completion or withdrawal) – (date of first dose in 205MS303) + 1 day.

6.3.3. Extent of Exposure for the 205MS302-205MS303 Study Population

The number of doses of DAC HYP received in the 205MS303 study and in total, per subject, will be summarized for all subjects combined.

Time on study (days) in the 205MS303 study will be computed for each subject as (date of study completion or withdrawal) – (date of first dose in 205MS303) + 1 day.

6.4. Concomitant Therapy

Medications (prescribed or over-the-counter) and non-drug therapies are considered concomitant if they are used during the study (i.e., either started prior to the study and continued while on study or started after the first dose of study treatment). Medications started more than 180 days after the last dose of study treatment are not considered concomitant. The World Health Organization (WHO) dictionary will be used for coding concomitant medication, and the Medical Dictionary for Regulatory Affairs (MedDRA) will be used for coding concomitant non-drug therapies.

The number and percentage of subjects taking any concomitant medications in 205MS303 will be reported for the 205MS301-303 safety population, the 205MS203-303 Safety Population, and the 205MS302-303 Safety Population, respectively. The most frequent concomitant medications, defined as those taken by at least 10% of subjects, and use of alternative MS medications and steroids may also be summarized.

The list of potential hepatotoxic medications is defined and agreed by SABR prior to data base lock. The number and percentage of subjects taking any potential hepatotoxic concomitant medications in 205MS303 will be reported for the 205MS301-303 safety population, the 205MS203-303 Safety Population, and the 205MS302-303 Safety Population, respectively.

7. Efficacy Data

7.1. Summary of Efficacy Analyses

Table 7 shows the overall summary of the efficacy analyses.

For the 205MS301-303 ITT population, efficacy analyses will be performed in the 205MS303 Treatment Period and the Combined Study Period. Selected analyses will be also done for the 205MS301-303 ITT population in the 205MS301 Treatment Period for evaluation with corresponding results in the 205MS303 Treatment period (e.g., for the annualized relapse rate). For the combined study period, data from the last dose of study treatment in 205MS301 to the first dose of study treatment in 205MS303 will also be included in the analysis.

For the 205MS203-303 ITT population, efficacy analyses will be performed in the 205MS303 Treatment Period, and will be summarized for all subjects combined. For the 205MS302-303 ITT population, efficacy analyses will be performed in the 205MS303 Treatment Period. Note that for subjects in the 205MS203-303 ITT population and the 205MS302-303 ITT population, due to the inherent difference in dosing and treatment in their previous studies, efficacy analyses will only be performed in the 205MS303 Treatment Period.

Table 7: Summary of populations and treatment periods for efficacy analyses

Population	Study/Treatment Period	Baseline
205MS301-303 ITT population	205MS301 Treatment Period	205MS301 Baseline
	205MS303 Treatment Period	205MS303 Baseline
	Combined Study Period	205MS301 Baseline
205MS203-303 ITT population	205MS303 Treatment Period	205MS303 Baseline
205MS302-303 ITT population	205MS303 Treatment Period	205MS303 Baseline

	Protocol 205MS303 Statistical Analysis Plan	Final Version 1.0
---	--	--------------------------

The following three tables include endpoints, analysis populations, baseline type with a short summary of statistical methods for the efficacy analyses. Sections below include more details about these analyses.

Table 8: Summary of efficacy analyzes for the 205MS301-303 ITT population

Endpoint	Population	Study/Treatment Period	Baseline	Statistical Methods
Annualized relapse rate	205MS301-303 ITT population	Combined Study Period	205MS301 Baseline	Unadjusted and adjusted ARR. Adjusted ARR will be estimated from the negative binomial model, adjusting for age, prior IFN beta, baseline EDSS and baseline relapse rate at the 205MS301 Baseline.
		205MS301 Treatment Period	205MS301 Baseline	As above
		205MS303 Treatment Period	205MS303 Baseline	As above. Covariates will include prior IFN beta at the 205MS301 Baseline, age at the 205MS303 Baseline, baseline EDSS, and the number of relapses in a year prior to 205MS303 baseline.
Annualized relapse rate by year	205MS301-303 ITT population	205MS301 Treatment Period	205MS301 Baseline	Unadjusted and adjusted ARR. Adjusted ARR will be estimated from the Poisson model, adjusting for age, prior IFN beta, baseline EDSS and baseline relapse rate at the 205MS301 Baseline.
		205MS303 Treatment Period	205MS303 Baseline	As above. Covariates will include prior IFN beta at the 205MS301 Baseline, age at the 205MS303 Baseline, baseline EDSS, and the number of relapses in a year prior to 205MS303 baseline.
Proportion of subjects who relapsed at selected time points	205MS301-303 ITT population	Combined Study Period	205MS301 Baseline	Kaplan-Meier curve of time to first relapse will be used to estimate the proportion at selected time points.
		205MS303 Treatment Period	205MS303 Baseline	As above
Proportion of subjects with 6-month sustained disability progression measured by EDSS at selected time points	205MS301-303 ITT population	Combined Study Period	205MS301 Baseline	Kaplan Meier analysis of time to the 6-month sustained disability progression will be used to estimate the proportion at selected time points.
		205MS303 Treatment Period	205MS303 Baseline	As above

**Protocol 205MS303
Statistical Analysis Plan**

Final Version 1.0

Endpoint	Population	Study/Treatment Period	Baseline	Statistical Methods
EQ-5D: EQ5D VAS, EQ-5D index score and EQ-5D individual questions	205MS301-303 ITT population	205MS303 Treatment Period	205MS303 Baseline	Descriptive statistics by previous treatment group in 205MS301 and by study visit in 205MS303.
MRI endpoints at selected visits of the 2015MS301 and 2015MS303 studies: 1) total number of new or newly-enlarging T2 hyperintense lesions 2) total number of new T1 hypointense lesions 3) total number of Gd lesion 4) total volume of T2 hyperintense lesions 5) the volume of new or newly enlarging T2 lesions 6) total volume of new T1 hypointense lesions 7) Percent Brain Volume Change (PBVC)	205MS301-303 ITT population	205MS301 Treatment Period	205MS301 Baseline	Descriptive statistics by previous treatment group in 205MS301 and by study visit in 205MS301 study. For the total number of new or newly enlarging T2 lesions and the total number of new T1 lesions: negative binomial model, adjusted for 301 baseline characteristics.
	205MS301-303 ITT population	205MS303 Treatment Period	205MS303 Baseline	Descriptive statistics by previous treatment group in 205MS301 and by study visit in 205MS303 study. For the total number of new or newly enlarging T2 lesions and the total number of new T1 lesions: negative binomial model, adjusted for 303 baseline characteristics. PBVC will be analyzed during the 205MS303 treatment period and with either 205MS301 or 205MS303 baseline.
EDSS: actual score and change from baseline	205MS301-303 ITT population	205MS303 Treatment Period	205MS303 Baseline	Descriptive statistics by previous treatment group in 205MS301 and by study visit in 205MS303.
MSFC z-score and component z-scores: actual value and change from baseline	205MS301-303 ITT population	Combined Study Period	205MS301 Baseline	Descriptive statistics by previous treatment group in 205MS301 and by study visit in 205MS301 and 205MS303. See section 8.4.3.
		205MS303 Treatment Period	205MS303 Baseline	Descriptive statistics by previous treatment group in 205MS301 and by study visit in 205MS303. See section 8.4.3.
PASA 3: actual value and change from baseline	205MS301-303 ITT population	Combined Study Period	205MS301 Baseline	Descriptive statistics by previous treatment group in 205MS301 and by study visit in 205MS301 and 205MS303.

**Protocol 205MS303
Statistical Analysis Plan**

Final Version 1.0

Endpoint	Population	Study/Treatment Period	Baseline	Statistical Methods
		205MS303 Treatment Period	205MS303 Baseline	Descriptive statistics by previous treatment group in 205MS301 and by study visit in 205MS303.
SDMT: actual score and change from baseline; proportion of subjects with a ≥ 3 or ≥ 4 decline from baseline; proportion of subjects with a ≥ 3 or ≥ 4 increase from baseline.	205MS301-303 ITT population	Combined Study Period	205MS301 Baseline	Descriptive statistics by previous treatment group in 205MS301 and by study visit in 205MS301 and 205MS303.
		205MS303 Treatment Period	205MS303 Baseline	Descriptive statistics by previous treatment group in 205MS301 and by study visit in 205MS303.
MSIS-29 physical score and MSIS-29 psychological score: actual score and change from baseline; proportion of subjects with a ≥ 7.5 worsening from baseline in MSIS-29 physical score.	205MS301-303 ITT population	205MS303 Treatment Period	205MS303 Baseline	Descriptive statistics by previous treatment group in 205MS301 and by study visit in 205MS303.
Proportion of subjects who are free from disease activity	205MS301-303 ITT population	205MS303 Treatment Period	205MS303 Baseline	Descriptive statistics by previous treatment group in 205MS301
HRU: MS-related and non-MS related visits	205MS301-303 ITT population	205MS301 Treatment Period		Descriptive statistics for the number of unscheduled site visits by previous treatment group in 205MS301 and by visit in 205MS301 study.
		205MS303 Treatment Period		Descriptive statistics for the number of unscheduled site visits by previous treatment group in 205MS301 and by visit in 205MS303 study.
HRPQ	205MS301-303 ITT population	205MS303 Treatment Period		Descriptive statistics by previous treatment group in 205MS301 and by study visit in 205MS303 study.

Table 9: Summary of efficacy analyzes for the 205MS203-303 ITT population

Endpoint	Study/Treatment Period	Baseline	Statistical Methods
Annualized relapse rate	205MS303 Treatment Period	205MS303 Baseline	Unadjusted and adjusted ARR for all subjects combined. Adjusted ARR will be estimated from the negative binomial/Poisson model, adjusting for baseline relapse rate at the 205MS303 Baseline
Annualized relapse rate by 48-week time interval	205MS303 Treatment Period	205MS303 Baseline	Unadjusted and adjusted ARR for all subjects combined. Adjusted ARR will be estimated from the Poisson model, adjusting for baseline relapse rate at the 205MS303 Baseline.
Proportion of subjects who relapsed at selected time points	205MS303 Treatment Period	205MS303 Baseline	Kaplan-Meier curve of time to first relapse will be used to estimate the proportion at selected time points for all subjects combined
Proportion of subjects with 6-month sustained disability progression measured by EDSS at selected time points	205MS303 Treatment Period	205MS303 Baseline	Kaplan Meier analysis of time to the 6-month sustained disability progression will be used to estimate the proportion at selected time points for all subjects combined
EDSS: actual score and change from baseline	205MS303 Treatment Period	205MS303 Baseline	Descriptive statistics by study visit in 205MS303 for all subjects combined.
EQ-5D: EQ5D VAS, EQ-5D index score and EQ-5D individual questions	205MS303 Treatment Period	205MS303 Baseline	Descriptive statistics by study visit in 205MS303 for all subjects combined.
MRI endpoints at selected visits of the 205MS303 study	205MS303 Treatment Period		Descriptive statistics by study visit in 205MS303 study for all subjects combined.
HRU: MS-related and non-MS related visits	205MS303 Treatment Period		Descriptive statistics for the number of unscheduled site visits by visit in 205MS303 study.
HRPQ	205MS303 Treatment Period		Descriptive statistics by study visit in 205MS303 study.

Table 10: Summary of efficacy analyzes for the 205MS302-303 ITT population

Endpoint	Study/Treatment Period	Baseline	Statistical Methods
Annualized relapse rate	205MS303 Treatment Period	205MS303 Baseline	Unadjusted and adjusted ARR. Adjusted ARR may be estimated from the negative binomial/Poisson model, adjusting for baseline relapse rate at the 205MS303 Baseline.
Annualized relapse rate by 48-week interval	205MS303 Treatment Period	205MS303 Baseline	Unadjusted and adjusted ARR. Adjusted ARR may be estimated from the Poisson model, adjusting for baseline relapse rate at the 205MS303 Baseline.
Proportion of subjects who relapsed at selected time points	205MS303 Treatment Period	205MS303 Baseline	Kaplan-Meier curve of time to first relapse will be used to estimate the proportion at selected time points.
Proportion of subjects with 6-month sustained disability progression measured by EDSS at selected time points	205MS303 Treatment Period	205MS303 Baseline	Kaplan Meier analysis of time to the 6-month sustained disability progression will be used to estimate the proportion at selected time points.
EDSS: actual score and change from baseline	205MS303 Treatment Period	205MS303 Baseline	Descriptive statistics by study visit in 205MS303.
EQ-5D: EQ5D VAS, EQ-5D index score and EQ-5D individual questions	205MS303 Treatment Period	205MS303 Baseline	Descriptive statistics by study visit in 205MS303.
MRI endpoints at selected visits of the 205MS303 study	205MS303 Treatment Period		Descriptive statistics by study visit in 205MS303 study.
HRU: MS-related and non-MS related visits	205MS303 Treatment Period		Descriptive statistics for the number of unscheduled site visits by visit in 205MS303 study.
HRPQ	205MS303 Treatment Period		Descriptive statistics by study visit in 205MS303 study.

	
Protocol 205MS303 Statistical Analysis Plan
	
Final Version 1.0

---	--	--

7.2. Annualized Relapse Rate

7.2.1. Annualized Relapse Rate in the 205MS301-303 ITT Population

In Study 205MS301, relapses were defined as new or recurrent neurological symptoms not associated with fever or infection, lasting at least 24 hours, and accompanied by new objective neurological findings upon examination by the *Examining Neurologist*. In addition, these relapses must have been reviewed and confirmed by the Independent Neurology Evaluation Committee (INEC).

In Study 205MS303, relapses are defined as new or recurrent neurological symptoms not associated with fever or infection, lasting at least 24 hours, and accompanied by new objective neurological findings upon examination by the *Study Neurologist*. The subject must have objective signs on the examination confirming the event.

Therefore, Studies 205MS301 and 205MS303 utilize essentially the same definition for objective (i.e., protocol-defined) relapses, with the exception that there is no Independent Neurology Evaluation Committee (INEC) in Study 205MS303. Because relapses in 205MS303 were not evaluated by an independent committee, all investigator-confirmed relapses from 205MS301 are included whether or not independently confirmed. New or recurrent neurological symptoms that occurred less than 30 days following the onset of a protocol-defined relapse will be considered part of the same relapse (i.e., relapses with onset days ≤ 29 days of one another, will be counted as 1 relapse).

The annualized relapse rate will be summarized using the following study population and study periods:

- 205MS301-303 ITT population in the combined study period
- 205MS301-303 ITT population in the 205MS301 Treatment Period and the 205MS303 Treatment period.

The relapse rate will be reported using relapses that occurred on or after the first dose date during the applicable study period. Relapses that occur after subjects receive alternative MS medications will be excluded from the analyses of relapse rate, and the subject's time on study will be censored at the time the alternative MS medication is added. For each analysis period, the subject's time on study will be censored at the time the alternative MS medication in the given period. For example, if a subject from the 205MS301-303 ITT population took alternative medication in the 205MS301 study before the first dose in study 205MS303 and in the 205MS303 study, this subject will be included in the analyses of the 205MS303 Treatment period and will be censored at the time the alternative MS medication in the 205MS303 study.

The unadjusted ARR will be calculated as the total number of relapses experienced during the given period, divided by the total number of days in the study period or the time of censoring, and the ratio then multiplied by 365.25. Relapse rate may be tabulated by the 205MS301 study treatment group (IFN β -1a 30 μ g and 150 mg DAC HYP).

	Protocol 205MS303 Statistical Analysis Plan	Final Version 1.0
---	--	--------------------------

For the combined study period and the 205MS301 Treatment Period, the relapse rate will also be estimated using a negative binomial model, with adjustment for the following characteristics at the 205MS301 Baseline: baseline relapse rate (number of relapses in the 3-years prior to study entry divided by 3), history of prior IFN β use (yes/no, collected as a stratification variable in IVRS), baseline EDSS (EDSS \leq 2.5 versus EDSS $>$ 2.5) and baseline age (age \leq 35 versus age $>$ 35). The logarithmic transformation of the number of days in the study will be included in the model as the “offset” parameter. If the data are under-dispersed (assessed using the Pearson Chi-Squared statistic) or if the negative binomial model does not converge, a Poisson regression model will be used instead. The Poisson model will be adjusted for over-dispersion using a Pearson scale parameter. The treatment group is the previous treatment group of the 205MS301 study. For the 205MS303 Treatment Period, a similar analysis will be done. The adjustment will be performed with the following characteristics: number of relapses in a year prior to the first dose in 205MS303, history of prior IFN β use at the 205MS301 baseline, age (age \leq 35 versus age $>$ 35) at the 205MS303 Baseline and EDSS (EDSS \leq 2.5 versus EDSS $>$ 2.5) at the 205MS303 Baseline.

To further assess the durability of treatment, the relapse rate will also be summarized by year for the 205MS301-303 ITT population in the 205MS301 Treatment Period and the 205MS303 Treatment Period. For these analyses, rates will be tabulated by evaluating the number of relapses in each time period and the amount of follow-up time in the time period. A Poisson model will be used to estimate the relapse rate in each time period unless data are over-dispersed in which case a negative binomial model will be used.

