5.2. Analysis of baseline data

The definition of baseline will be dependent on the analysis performed and the cohort of patients utilized. The following are the various definitions of baseline that may be used in the analyses:

5.2.1. 205MS301-205MS303 Study Baselines

205MS301 Baseline

Study 205MS301 Baseline is defined as the latest available value prior to or on the date of the first dose of study treatment in Study 205MS301.

205MS303 Baseline

Study 205MS303 Baseline is defined as the latest available value prior to or on the date of the first dose of study treatment in Study 205MS303.

Demographic characteristics, baseline disease characteristics and medical history will be summarized using the 205MS301-303 ITT population at the 205MS301 Baseline and at the 205MS303 Baseline.

DAC HYP Baseline

DAC HYP Baseline is equal to the 205MS301 baseline for subjects randomized to DAC HYP in 205MS301, or the 205MS303 baseline for subjects randomized to IFN β -1a in 205MS301. If no assessments, or if multiple measurements were performed on the day of first dose of DAC HYP, the last measurement prior to the first dose of DAC HYP will be used.

Unless otherwise specified, the DAC HYP Baseline will be utilized in measurements for safety assessments such as laboratory values and vital signs.

5.2.2. 205MS203-205MS303 Study Baselines

205MS303 Baseline is defined as the latest available value prior to or on the date of the first dose of study treatment in Study 205MS303.

DAC HYP Baseline

Subjects enrolled from 205MS203 study had completed the 205MS201, 205MS202, and 205MS203 studies. For subjects randomized to DAC HYP either 150 mg or 300 mg in 205MS201, the DAC HYP Baseline is defined as the 205MS201 baseline. For subjects randomized to placebo in 205MS201, the DAC HYP Baseline is defined as the 205MS202 Baseline. If no assessments, or if multiple measurements were performed on the day of first dose of DAC HYP, the last measurement prior to the first dose of DAC HYP will be used.

	Protocol 205MS303 Statistical Analysis Plan	Final Version 1.0
---	--	--------------------------

5.2.3. 205MS302-205MS303 Study Baselines

205MS303 Baseline

Study 205MS303 Baseline is defined as the latest available value prior to or on the date of the first dose of study treatment in Study 205MS303.

DAC HYP Baseline

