5.3. Key Dates Time Period Definitions

The following time periods will be defined for efficacy and safety analyses:

205MS301 Treatment Period

The 205MS301 Treatment Period is the time period as defined in the 205MS301 statistical analysis plan and includes data collected from the first dosing date to the end of treatment period visit in the 205MS301 study. For subjects who completed study treatment this is the date of the last scheduled treatment period visit in that study.

205MS303 Treatment Period refers to the time between the first dose date in 205MS303 and the date of the last available measurement prior to 180 days after the last dose date in 205MS303. This is the time period for most of the efficacy analyses and for all the safety analyses for all the populations.

Combined Study Period

For the 205MS301-303 ITT population, the Combined Study Period is the combined period of the 205MS301 and 205MS303 studies, that is the time between the first dose date in 205MS301 and the date of the last available measurement prior to 180 days after last dose date in 205MS303.

Note that for the 205MS203-303 ITT population and the 205MS302-303 ITT population, the combined study period is not necessary due to the limited number of patients in each population.

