7.2.2. Annualized Relapse Rate in the 205MS203-303 ITT Population

The annualized relapse rate will be summarized for the 205MS203-303 ITT population in the 205MS303 Treatment period. The relapse rate will be reported using relapses that occurred on or after the first DAC HYP dose date in the 205MS303 Treatment period. Relapses that occur after subjects receive alternative MS medications will be excluded from the analyses of relapse rate, and the subject’s time on study will be censored at the time the alternative MS medication is added.

The unadjusted ARR will be calculated as the total number of relapses experienced during the given period, divided by the total number of days in the period or the time of censoring, and the ratio then multiplied by 365.25. Relapse rate will be tabulated for all subjects combined.

For the 205MS303 Treatment period, the relapse rate will also be estimated using a negative binomial model, with adjustment for the number of relapses in a year prior to the first dose in 205MS303. The logarithmic transformation of the number of days in the study will be included in the model as the “offset” parameter. If the data are under-dispersed (assessed using the Pearson Chi-Squared statistic) or if the negative binomial model does not converge, a Poisson regression model will be used instead. The Poisson model will be adjusted for over-dispersion using a Pearson scale parameter.

To further assess the durability of treatment, the relapse rate will also be summarized by 48-week time intervals defined in the 205MS303 Treatment Period. For these analyses, rates will be tabulated by evaluating the number of relapses in each time interval and the amount of follow-up time in the time interval. A Poisson model will be used to estimate the relapse rate in each time interval unless data are over-dispersed in which case a negative binomial model will be used.

	Protocol 205MS303 Statistical Analysis Plan	Final Version 1.0
---	--	--------------------------

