The total number of T2 lesions at 205MS303 baseline will be calculated by summing the 205MS301 baseline number of T2 lesions and the number of new or newly enlarging lesions since the previous visit at 205MS301 Week 24, 205MS301 Week 96, 205MS301 Week 144 (if available) and 205MS303 Baseline (if available). The same algorithm will be applied to the total number of T1 lesions and the total volume of T1 lesions at 205MS303 baseline.

Data obtained after alternative MS medication will be set to missing. Missing data will not be imputed.

The total number of new or newly enlarging T2 hyperintense lesions

The number of new or newly-enlarging T2 hyperintense lesions relative to the 205MS301 baseline will be analyzed for Week 24 and Week 96 of the 205MS301 study. The number of new or newly-enlarging T2 hyperintense lesions relative to the 205MS303 baseline will be analyzed for Weeks 48, 96, 144, 192, and 240 (if available) of the 205MS303 study.

A negative binomial regression model will be used to analyze the observed new or newly enlarging T2 lesions. The model for the analysis relative to the 205MS301 baseline will be adjusted for the following characteristics at the 205MS301 baseline: volume of T2 hyperintense lesions, history of prior IFN β use and baseline age (age \leq 35 versus age $>$ 35). The model for the analysis relative to

	Protocol 205MS303 Statistical Analysis Plan	Final Version 1.0
---	--	--------------------------

the 205MS303 baseline will be adjusted for the following characteristics: the volume of T2 hyperintense lesions at the 205MS303 baseline, history of prior IFN β use at the 205MS301 baseline, and baseline age (age \leq 35 versus age $>$ 35) at the 205MS303 baseline.

The total number of new T1 hypointense lesions

The total number of new T1 hyperintense lesions relative to the 205MS301 baseline and the 205MS303 baseline will be analyzed using the same methodology as for the analysis new or newly-enlarging T2 hyperintense lesions. The estimated number of lesions will be evaluated using negative binomial regression, adjusted for the history of prior IFN β use at the 205MS301 baseline, age (age \leq 35 versus age $>$ 35) at the corresponding baseline, and volume of T1 hypointense lesions at the corresponding baseline.

Number of Gd-Enhancing Lesions

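### For subjects already on DAC HYP in 205MS301, the yearly relapse rates meant to show durability restart at 205MS303 entry and mix roughly the third and fourth treatment years

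*SAP*

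**What the plan says.** Section 7.2.1 states the analysis together with its purpose: "To further assess the durability of treatment, the relapse rate will also be summarized by year for the 205MS301-303 ITT population". The tabulation is made separately within each study's treatment period. The by-year rows of Table 8 list the same two periods, each with its own study baseline, and no by-year row for the Combined Study Period.

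Section 5.3 sets the clock for the second period: "205MS303 Treatment Period refers to the time between the first dose date in 205MS303 and the date of the last available measurement". The 205MS301 Treatment Period closes at that study's end-of-treatment visit.

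Section 5.2.1 already defines a reference point tied to the start of the drug: "DAC HYP Baseline is equal to the 205MS301 baseline for subjects randomized to DAC HYP in 205MS301". In the prior IFN beta-1a arm it coincides with entry into 205MS303. Its stated use is for safety: "Unless otherwise specified, the DAC HYP Baseline will be utilized in measurements for safety assessments such as laboratory values and vital signs". Table 7 lists only the 205MS301 and 205MS303 baselines for efficacy.

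On presentation, Section 5.4 says that summaries for this cohort are in general shown by previous 205MS301 treatment group, and Section 7.2.1 makes that group the treatment term in the model. The ARR text itself only permits tabulation by that group, and the by-year rows of Table 8 name no split.

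**The concern.** Durability is a question about time on DAC HYP: does the relapse rate hold, fall or rise as treatment continues? Yearly rows answer it cleanly only if each row holds subjects at the same stage of treatment.

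In the prior DAC HYP arm they do not. A subject who left 205MS301 at about Week 96 and one who left at about Week 144 both enter 205MS303 Year 1, although they are about one treatment year apart. Conversely, treatment weeks 96 to 144 sit in the 205MS301 rows for the second subject and in the 205MS303 rows for the first. Any trend across those years is averaged within rows, in the arm with the longest exposure.

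The gap between the studies is a second break. It lies after the 205MS301 Treatment Period and before the 205MS303 Treatment Period, so its time and relapses appear in no yearly row. Section 7.1 does include data between the last 205MS301 dose and the first 205MS303 dose in the Combined Study Period, but no yearly ARR is planned there.

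**Working it through.** The SAP states no rate, sample size or power for this analysis, so there is no planned figure to reproduce. The check is arithmetic on the time axis.

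**Inputs**
- Time in 205MS301 before entry, *L*: about 96 to 144 weeks for the DAC HYP arm. This is inferred from Section 7.6.1. That section accepts a 205MS301 Week 96 MRI taken up to 28 days after the first 205MS303 dose, so some subjects entered at about Week 96. It also counts "205MS301 Week 144 (if available"), so others stayed to about Week 144. The SAP gives no distribution of *L*.
- Gap, *g*: 0 to 26 weeks. Table 1, footnote 3 allows entry up to 6 months after completing 205MS301; 6 months is taken as 26 weeks.
- Year: 48 weeks, as the schedule tables label it (Week 48 starts Year 2, Week 96 starts Year 3). Section 7.2.1 does not define it.
- IFN beta-1a arm: DAC HYP starts at 205MS303 entry, so the offset is 0.

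**Formula**

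Week since first DAC HYP dose = *L* + *g* + week in 205MS303, with *L* = *g* = 0 for the IFN beta-1a arm.

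**205MS303 Year 1 (weeks 0 to 48) on the DAC HYP clock**

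| Prior arm | *L* | *g* | Weeks since first dose |
|---|---|---|---|
| DAC HYP | 96 | 0 | 96–144 (3rd interval) |
| DAC HYP | 144 | 0 | 144–192 (4th interval) |
| DAC HYP | 96 | 26 | 122–170 |
| DAC HYP | 144 | 26 | 170–218 |
| IFN beta-1a | 0 | 0 | 0–48 (1st interval) |

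**Spread of starting points within the DAC HYP arm**
- No gap: 144 − 96 = 48 weeks.
- Gap counted: (144 + 26) − 96 = 74 weeks.

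If the optional prior-arm split were not made, the difference between arms within one row would be 96 to 144 weeks, or up to 170 with the gap.

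**Illustration of the consequence.** None of these rates is in the SAP. Assume 0.30 relapses per year in the first DAC HYP interval, half the DAC HYP arm entering at Week 96 and half at Week 144, no gap, and arms of equal size.
- No trend: every row is 0.30. No bias.
- 15% fall per interval: interval 3 = 0.30 × 0.85² = 0.217; interval 4 = 0.30 × 0.85³ = 0.184. The DAC HYP arm's Year 1 row reads (0.217 + 0.184)/2 = 0.200, and the IFN beta-1a arm's row reads 0.300. Pooled over arms it would read 0.250.
- 30% fall per interval: interval 3 = 0.147, interval 4 = 0.103, row = 0.125; IFN beta-1a row 0.300; pooled 0.212.

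Within the DAC HYP arm, the blurring is thus about half the change between two adjacent intervals. Pooling over arms would do more damage than mixing within the arm.

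**The case against.** The best defence has four parts.

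1. **Most rows are already on the right clock.** Under the general rule to present by prior arm, switchers' 205MS303 years are their DAC HYP years and continuers' 205MS301 years are theirs. This stands. A reader might infer that switchers and continuers cannot be compared on one treatment-time axis at all; the definitions in Section 5.2.1 do not support that. Only continuers' rows from 205MS303 onward are affected. The split is, however, only optional in the ARR text.

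2. **The size is easily inflated.** From the earliest row start to the latest row end is 218 − 96 = 122 weeks, and 122/48 is about 2.5, so a reader might infer that 2.5 treatment years are pooled. But a perfectly aligned row already spans 48 of those weeks, and up to 26 are gap time between the studies. Without the gap the row covers the third and fourth intervals and nothing later.

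3. **There is a first-dose clock elsewhere.** Combined Study Period ARR and time to first relapse start at the first 205MS301 dose, which is the start of DAC HYP for continuers. True, but the first is a single average and the second follows only the first event; neither shows the rate by treatment year.

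4. **It is descriptive.** Section 5.4 says that analyses are generally descriptive, rates by study year are a legitimate summary, and bias needs a trend. This stands and sets the weight of the point. A trend is nevertheless what a durability analysis is meant to reveal.

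The same criticism might seem to carry over to the cohorts from 205MS203 and 205MS302, where Section 7.2.2 says that "the relapse rate will also be summarized by 48-week time intervals defined in the 205MS303 Treatment Period". The SAP does not give the lengths of their parent studies, and Section 7.1 restricts their efficacy analyses to 205MS303 because earlier dosing and treatment differed. The point is not made for them.

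**Conclusion.** The point holds for the prior DAC HYP arm of the 205MS301-303 ITT population. Its 205MS303 yearly rows combine subjects whose treatment start differs by up to 48 weeks, or 74 weeks since first dose when the gap is counted. Year 1 therefore blends roughly the third and fourth 48-week intervals, and the 205MS301 and 205MS303 rows do not form one durability curve. Prior IFN beta-1a subjects are not affected.

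This rests on the 96-to-144-week range, which is read from MRI visits because the SAP does not state treatment length, and on 6 months being about 26 weeks. If nearly all subjects entered at similar times, the mixing would be small. If the relapse rate is constant over treatment time, there is no bias. No test, error rate or primary endpoint is touched. It is a cheap improvement to a secondary descriptive analysis.

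**What to change.** In Section 7.2.1 and Table 8:

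- Add ARR, unadjusted and model-based, by 48-week interval since the first DAC HYP dose (the point to which the DAC HYP Baseline is tied), by prior 205MS301 arm. Use 205MS301 plus 205MS303 time for the prior DAC HYP arm, and 205MS303 time only for switchers.
- Make the split by prior arm mandatory for the by-year ARR, in place of the present permissive wording.
- For the prior DAC HYP arm, include between-study time and relapses, as Section 7.1 does for the Combined Study Period, and add a sensitivity version that excludes them.
- Keep the by-study-year table as supportive.

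Section 7.2.1 already aligns the relapse definition across the two studies by counting all investigator-confirmed 205MS301 relapses, so joining the person-time needs no new rule for events. The cost is SAP wording and a re-cut of dates already held. The drawback is that later intervals will have fewer subjects and wider confidence intervals.
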